	≤ 25% ZP patch application site has punctate bruising spots	1 (1.2%)	5 (6.4%)	9 (10.7%)	4 (4.8%)
	≥ 26% to < 50% ZP patch application site has punctate bruising spots	0 (0.0%)	0 (0.0%)	2 (2.4%)	2 (2.4%)
	> 50% ZP patch application site has punctate bruising spots	0 (0.0%)	0 (0.0%)	1 (1.2%)	3 (3.6%)
Edema	N	83	78	84	83
	None	83 (100.0%)	77 (98.7%)	81 (96.4%)	82 (98.8%)
	Slight Edema	0 (0.0%)	1 (1.3%)	3 (3.6%)	1 (1.2%)
	Moderate Edema	0 (0.0%)	0 (0.0%)	0 (0.0%)	0 (0.0%)
	Severe Edema	0 (0.0%)	0 (0.0%)	0 (0.0%)	0 (0.0%)
Erythema	N	83	78	84	83
	None	78 (94.0%)	71 (91.0%)	71 (84.5%)	64 (77.1%)
	Mild Redness	5 (6.0%)	7 (9.0%)	10 (11.9%)	16 (19.3%)
	Well-defined Redness	0 (0.0%)	0 (0.0%)	3 (3.6%)	3 (3.6%)
	Beet Redness	0 (0.0%)	0 (0.0%)	0 (0.0%)	0 (0.0%)

Subjects' ratings of the application sites for erythema, edema, and bruising are shown in the following figures (note that the number of subjects who entered values for 4, 12, and 48 hours was smaller than at 30 minutes and 24 hours, as amendment #3 which required the addition of 4, 12, and 48 hour assessments was implemented mid-study).

Figure 4: Subject-reported Patch Application Site Reactions (Redness, Bruising, and Swelling)

[figure not shown]

Figure 5: Subject Reported Patch Application Bruising

[figure not shown]
[figure not shown]

Figure 6: Subject Reported Patch Application Swelling

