4.1.2 Product Description and Patch Application

The Zosano M207 Intracutaneous Microneedle System is a novel drug delivery technology which consists of a disposable titanium patch centered on an adhesive backing with microneedles that are dry-coated with the drug product formulation, and a reusable handheld applicator that ensures that the patch is applied with a defined application speed and energy to the site of administration.

The M207 Intracutaneous Microneedle System is a proprietary disposable patch and a reusable applicator. The zolmitriptan-coated titanium microneedle array (3 cm² array) is attached to a 5 cm² adhesive patch (Figure 8). A magnified image of the zolmitriptan-coated microneedles is shown in Figure 8. The patch system is composed of several parts. The patch is mounted inside a polycarbonate plastic ring with a co-molded desiccant (Figure 9).

The M207 drug product used in CP-2017-001 is packaged in a nitrogen purged foil pouch or cup (see Figure 10). The reusable applicator is shown in Figure 9 and Figure 10 with a lock-out function to avoid accidental firing. The applicator provides a spring-driven piston to apply the patch with consistent impact energy of 0.26 Joules. The user presses the handheld reusable applicator onto the patch ring assembly for attachment, then the applicator is un-locked by twisting the cap. The user applies the patch by pressing the applicator/patch ring assembly onto the skin site and holding it to the arm for 3 seconds (Figure 10).

Figure 8: 5 cm² Patch with Zolmitriptan Coated Titanium Microneedle Array

[figure not shown]

Figure 9: Handheld Gen 6 Patch Ring Assembly and Applicator

[figure not shown]
[figure not shown]

Figure 10: *M207 Patch Application

	
Open the foil pouches or cups (depending on the kit dispensed).

	
Snap one patch-ring assembly onto the applicator.

	
Twist applicator cap clockwise from Position 1 to Position 2 to unlock for patch application.

	
Press applicator downward to apply patch to upper arm. Press down firmly against the skin until you hear a click then hold for 3 seconds. Patches are left on for 30 minutes.

	
Remove the outer ring in order to load and apply the second patch.

	
Repeat all of the above steps to apply second patch next to the first patch.

*See subject training video and instructions for use for exact instructions on how to apply the patches

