6 STUDY PROCEDURES AND SCHEDULE

6.1 Study Schedule

A schedule of study procedures is presented in [Table 10](#).

Table 10: Schedule of Study Procedures

Procedure	VISIT 1 ₁ Screening	VISIT 2 ₁ Start of Run-In	VISIT 3	VISIT 4, 5, 6	VISIT 7	VISIT 8	VISIT 9 Final visit or ET	VISIT 10 Two Week Post Study Visit
	Up to 1 week prior to Run-in	Week -2 (up to -3)	Day 1 (dispense patches)	Month 1, 2, 3	Month 6	Month 9	Month 12	Two Week Safety visit
Day/Visit Windows				Day 28, 56, 84 ± 7 days	Day 168 ± 7 days	Day 252 ± 7 days	Day 336 ± 7 days	14 (+ up to 14) days following final visit or ET
Week				Week 4, 8, 12	Week 24	Week 36	Week 48	Week 50 - 52
Informed Consent	X							
Inclusion/Exclusion/ Eligibility Criteria	X	X	X					
Med History/ Migraine History	X							
Fitzpatrick Skin Scale (subject completed)	X							
Demographics	X							
Physical Exam ₃	X		X		X		X	
Weight/Height (Height only at screen and final visit or ET) ₄	X		X	X		X	X	
Vital Signs ₅	X	X	X	X	X	X	X	X
Lab Chem/Hematology (fasting)	X ₆						X	
Serum or Urine Pregnancy (only for WOCP)	X - Serum		X - Urine	X - Urine	X - Urine	X - Urine	X - Urine	
Drug Abuse Testing	X				X		X	
12-lead ECG	X				X		X	
Train Subject on How to Apply Patches (using demo patches)		X	X					

Procedure	VISIT 1 ₁ Screening	VISIT 2 ₁ Start of Run-In	VISIT 3	VISIT 4, 5, 6	VISIT 7	VISIT 8	VISIT 9 Final visit or ET	VISIT 10 Two Week Post Study Visit
	Up to 1 week prior to Run-in	Week -2 (up to -3)	Day 1 (dispense patches)	Month 1, 2, 3	Month 6	Month 9	Month 12	Two Week Safety visit
Train/dispense eDiary		X	X					
Dispense Study Medication			X	X	X	X		
Study Drug Self-Administration								
Subject eDiary Reported Skin Assessments								
Migraine-ACT (subject completed)				X	X	X	X	
Investigator Skin Assessments				X	X	X	X	X
Monthly phone contacts to subject ⁷								
Collect Unused Patch(es)/Perform Drug Accountabilities ⁸				X	X	X	X	
Collect and Review eDiary data			X	X	X	X	X	
Record Adverse Events	X	X	X	X	X	X	X	X
Record Concomitant Medications	X	X	X	X	X	X	X	X

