 - Subject reported skin assessment for bruising, swelling, and/or redness (at 30 minutes, 2 hours, 12 hours, 24 hours and 48 hours post patch administration time points only)
 - Subject reported skin pain and skin itching at 48 hours post patch administration
- Dispense the Subject Skin Grading Card (Appendix 4) with the eDiary and instruct the subject to refer to this card when grading their skin reaction(s)/symptom(s) in the eDiary. The Grading Card will include a subject reminder to contact the study physician if he/she experiences any serious or severe skin reaction(s) at any time point or for worsening or non-resolving reactions at approximately 3 days post patches application (at 72 hours). In addition, the eDiary will remind the subject to call the study physician if he/she experiences any skin reaction(s) and/or symptom(s) at the patch application site which worsens rather than improves over approximately a five-day period. If the subject

contacts the study physician at any time point for worsening or non-resolving reactions, the subject must be seen for an unscheduled visit. The skin reaction(s)/symptom(s) will be assessed, recorded as an adverse event in the eCRF and followed to resolution.

6.1.5 Month 1 (Visit 4), Month 2 (Visit 5), Month 3 (Visit 6), Month 6 (Visit 7)

Visits must be scheduled to occur on (or within ± 7 days) of the protocol specified study day, ie, on study days 28 (Month 1), 56 (Month 2), 84 (Month 3), and 168 (Month 6). The following procedures will be performed at each visit:

- Administer the Migraine Assessment of Current Therapy (Migraine-ACT) which is completed by the subject
- Collect any unused patches, perform accountability, and dispense patches with applicator
- Perform physical exam, (Month 6 only) (height does not need to be recorded)
- Record vital signs: temperature, respiratory rate (RR), blood pressure (BP), and heart rate (HR)
- Collect urine for urine pregnancy test for all WOCBP
- Collect urine for drug abuse testing (Month 6 only)
- Perform 12-lead electrocardiogram (ECG) (Month 6 only)
- Ensure subject is dispensed the Subject Skin Grading Card (to be used with eDiary entries).
- Collect and review subject's eDiary data with the subject for the following:
 - Subject compliance with study drug treatment and subject responses in eDiary

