6.2.13 Subject Reported and Investigator Reported Skin Assessments

Subject reported bruising, bleeding (at 30 minutes only), erythema, edema, skin itching and skin pain are collected through the eDiary and will also be recorded as adverse events in the eCRF. The subject is also provided a Subject Skin Grading Card to help him/her assess whether they have any skin reaction(s) and how to grade any reaction(s) (see [Appendix 4](#)). If the subject contacts the investigator at any time point for worsening or non-resolving reactions, the subject must be seen for an unscheduled visit. The skin reaction(s)/symptom(s) will be assessed, recorded as adverse events in the eCRF and followed to resolution.

In addition, investigator skin assessments in [Section 6.2.13.1](#) will be completed at each in-clinic visit during the treatment period. Any findings related to the upper arm(s) where the patches were applied will be recorded as an adverse event in the eCRF and followed until the signs/symptoms resolve.

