APPENDIX 6 – Investigator Assessment Rating for Bruising, Erythema, Edema and

The Bruising, Erythema, and Edema assessment will be performed by the investigator at each in clinic visit starting at Month 1 and performed using the following ratings. When determining the percentage of application sites affected for a given sign, the investigator should consider the entire outer arm from the top of the shoulder to the elbow as the denominator. Any findings with ratings of 1 (mild), 2 (moderate), or 3 (severe) must be recorded as an adverse event in the eCRF and followed to resolution. The investigator will use the definitions of AE Severity Ratings for Mild, Moderate, Severe, Life-Threatening ([Section 8.2.1.3](#)) to assess the Severity of the AE.

Symptom	Rating (circle)
M207 application sites have bruising spots?	0 (clear) = None 1 (mild) = $\leq 25\%$ Present in the upper arm region of all M207 applications 2 (moderate) = ≥ 26 to $\leq 50\%$ Present in the upper arm region of all M207 applications 3 (severe) = $> 50\%$ Present in the upper arm region of all M207 applications

Symptom	Rating (circle)
Skin Erythema	0 (clear) = None 1 (mild) = $\leq 25\%$ Present in the upper arm region of all M207 applications 2 (moderate) = ≥ 26 to $\leq 50\%$ Present in the upper arm region of all M207 applications 3 (severe) = $> 50\%$ Present in the upper arm region of all M207 applications

Symptom	Rating (circle)
Skin Edema	0 (clear) = None 1 (mild) = $\leq 25\%$ Present in the upper arm region of all M207 applications 2 (moderate) = ≥ 26 to $\leq 50\%$ Present in the upper arm region of all M207 applications 3 (severe) = $> 50\%$ Present in the upper arm region of all M207 applications

The photographs below for bruising, erythema, and edema are examples for the investigator as to what these skin reaction(s) in the upper arm region may look like. The investigator will use the definitions of AE Severity Ratings for Mild, Moderate, Severe, Life-Threatening ([Section 8.2.1.3](#)) to assess the Severity of the AE.

[figure not shown]
Bruising

None (Clear)

Mild

Moderate

Severe

Erythema

[figure not shown]
None (Clear)

Mild

Moderate

Severe

Edema

[figure not shown]
None (Clear)

Mild

Moderate

Severe

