4.2. SAFETY ENDPOINTS

- Changes from baseline in physical examination findings at Months 6 and 12
- Changes from baseline in vital signs at Months 1, 2, 3, 6, 9, 12, and at the 2-week post-study visit
- Changes from baseline in clinical laboratory parameters at Month 12
- Changes from baseline and/or shifts in 12-lead ECG parameters at Months 6 and 12
- Frequency of concomitant medications

- Incidence of treatment-emergent systemic and skin AEs (TEAEs)
- Frequencies of type of redness, severity of swelling, amount of bruising, and amount of bleeding (30 minutes only) at the application site as reported by the subject at 30 minutes, 2 hour, 12 hour, 24 hour, and 48 hours post-dose
- Frequencies of amount of skin itching and severity of pain at the application site as reported by the subject at 48 hours post-dose
- Frequencies of amount of bruising, erythema, and edema at the application site as assessed by the Investigator at Months 1, 2, 3, 6, 9, 12, and at the 2-week post-study visit
- Proportion of subjects with presence of skin signs and symptoms as assessed by the Investigator at Months 1, 2, 3, 6, 9, 12, and at the 2-week post-study visit

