11.2.2. Investigator Skin Assessments

The investigator skin assessment will be made at each in clinic visit starting at month 1. The entire surface area of the outer upper arm from the upper shoulder to the elbow will be assessed for the following skin signs or symptoms.

Investigator reported skin bruising, skin redness (erythema), and skin swelling (edema) at the application site will be collected and will also be recorded in the eCRF.

The amount of bruising, erythema, and edema and the presence of skin signs and symptoms will be categorized and assessed as follows:

Skin signs or symptoms	Indicate arm assessed: Subject's Left and/or Right (circle)
Blisters or pustules?	Present: Yes or No If Yes, describe:
Scaly or flakey skin?	Present: Yes or No If Yes, describe:
Erosions or open sores?	Present: Yes or No If Yes, describe:
Scarring?	Present: Yes or No If Yes, describe:
Hyperpigmentation or Hypopigmentation?	Present: Yes or No If Yes, describe:

Bruising assessments (visual rating) will be performed using the following ratings:

Symptom	Rating (circle)
M207 application sites have bruising spots?	0 (clear) = None 1 (mild) = ≤ 25% Present in the upper arm region of all M207 applications 2 (moderate) = ≥ 26 to ≤ 50% Present in the upper arm region of all M207 applications 3 (severe) = > 50% Present in the upper arm region of all M207 applications

Erythema Severity Categories:

Symptom	Rating (circle)
Skin Erythema	0 (clear) = None 1 (mild) = ≤ 25% Present in the upper arm region of all M207 applications 2 (moderate) = ≥ 26 to ≤ 50% Present in the upper arm region of all M207 applications 3 (severe) = > 50% Present in the upper arm region of all M207 applications

Edema Severity Categories:

Symptom	Rating (circle)
Skin Edema	0 (clear) = None 1 (mild) = ≤ 25% Present in the upper arm region of all M207

	
applications
 
2 (moderate) = ≥ 26 to $\leq 50\%$ Present in the upper arm region of all M207 applications
 
3 (severe) = $> 50\%$ Present in the upper arm region of all M207 applications

--	---

The frequencies of amount of bruising, erythema, and edema at the application site as assessed by the Investigator at Months 1, 2, 3, 6, 9, 12, and at the 2-week post-study visit will be summarized. The proportion of subjects with any amount of all 3 symptoms (erythema, edema, and bruising) and all combinations of the 3 symptoms will be summarized by time point.

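### Investigator skin grades are percentages of the whole outer arm but are labelled as application-site amounts, and the mean time to resolution has no rule for unresolved events

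*Protocol*

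**What the plan says.** **Extent.** Protocol Appendix 6 instructs that "the investigator should consider the entire outer arm from the top of the shoulder to the elbow as the denominator", although the same sentence opens by speaking of the share of application sites affected. The rating rows use a third wording, the part of the upper arm covering all M207 applications. Grade 1 is up to 25%, grade 2 is 26% to 50%, and grade 3 is above 50%. Protocol 6.2.13.2, 6.2.13.3 and SAP 11.2.2 repeat these rows without the denominator sentence. Protocol 6.2.13.1 and SAP 11.2.2 say that the whole outer upper arm is inspected.

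The reported quantity is worded differently. SAP 4.2, like Protocol 7.1.1, lists "Frequencies of amount of bruising, erythema, and edema at the application site as assessed by the Investigator". SAP 11.2.2 says: "The frequencies of amount of bruising, erythema, and edema at the application site as assessed by the Investigator". The output is Table 14.3.2.3, by visit.

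**Duration.** SAP 11.2 will summarize the average number of days to resolution for eDiary-reported AEs. Protocol 8.4 follows non-serious skin AEs, subject to the investigator's judgment, until 14 days after the safety visit, and then records unresolved ones as ongoing. SAP 6.3 imputes nothing unless stated. No rule for ongoing events is given, and the SAP table index lists no table for this summary. The shells are a separate document.

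**The concern.** Long-term safety is the primary objective, and the effect of repeated application is the study's stated rationale. eDiary skin ratings stop at 48 hours after a dose. Beyond that, Table 14.3.2.3 is the only planned summary of graded extent, and the mean time to resolution is the only planned summary of how long reactions last.

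A reader who takes the label of Table 14.3.2.3 literally would read grade 1 as less than about a quarter of the patch site. That is close to what the lowest non-zero eDiary bruising category means in the same trial, and what the lowest non-zero bruising category meant in the earlier study. Here grade 1 means something else. A mean taken over resolved events only leaves out the longest ones.

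**Working it through.** The plan states no figure to reproduce, and SAP 3.5 says the sample size had no statistical basis. Two checks apply.

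**1. What one dose can score on the whole-arm scale**

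Inputs: the array "is attached to a 5 cm² adhesive patch" (Protocol 4.1.2); two patches per dose; cut-points from Appendix 6. Outer-arm area is not in the documents and is assumed to be 150 to 500 cm².

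- Area of one fully affected dose: 2 × 5 = 10 cm². The adhesive area is the generous choice; the arrays alone give 2 × 3 = 6 cm².
- Largest arm on which it exceeds grade 1: 10/0.26 = 38.5 cm². It is grade 1 on any arm of at least 10/0.25 = 40 cm², four times the dose's own area. This result does not need the assumed arm area.
- At the assumed areas: 10/150 = 6.7% and 10/500 = 2.0%, both grade 1.
- Fully affected, non-overlapping doses needed at once for grade 2: 0.26 × 150/10 = 3.9, so 4; 0.26 × 500/10 = 13.
- With the site as denominator, the same dose is 100%, which is grade 3.

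Comparison with the earlier study (Protocol Table 9): its top bruising category was "> 50% ZP patch application site has punctate bruising spots". At 3.8 mg, 4 + 2 + 3 = 9 of 83 subjects had bruising. Of these, 2 + 3 = 5 (5/83 = 6.0%) had at least 26% of the site affected, 3 of them more than 50%. On the present scale all 9 would be grade 1 if that dose were the only one affected, the bruising stayed within its sites and the arm were at least 40 cm². Only bruising can be compared in this way, because the earlier erythema and edema scales graded intensity.

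**2. What the mean duration leaves out**

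Unused patches are collected at the final visit (Protocol 6.1.6), so the last dose is no later than that day. The last eDiary skin report is 2 days after a dose. Visit 10 is 14 to 28 days after the final visit (Protocol 6.1.8). The minimum length of an eDiary-reported event still ongoing is then:

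| Last contact | Arithmetic | Minimum days |
|---|---|---|
| Visit 10 at day 14 | 14 − 2 | 12 |
| Visit 10 at day 28 | 28 − 2 | 26 |
| 8.4 cut-off, Visit 10 at day 14 | 14 + 14 − 2 | 26 |
| 8.4 cut-off, Visit 10 at day 28 | 28 + 14 − 2 | 40 |

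Early termination visits fall at least 7 days after the last patch, which adds 7 days to each row. Subjects lost to follow-up before Visit 10 are not covered.

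If a share *u* of events is unresolved, resolved events average *m* days and unresolved ones last at least *L* days, the resolved-only mean is too low by at least *u* × (*L* − *m*). Illustration only, with *m* assumed between 1 and 7 days:

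- *u* = 1%: with *L* = 12, 0.01 × (12 − 7) = 0.05 to 0.01 × (12 − 1) = 0.11 days; with *L* = 26, 0.19 to 0.25 days.
- *u* = 10%: with *L* = 12, 0.5 to 1.1 days; with *L* = 26, 1.9 to 2.5 days.

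The bias can also be negligible. With exponential durations of true mean 5 days and 28 days of follow-up, *p* = exp(−28/5) = 0.4% remain ongoing and the resolved-only mean is 5 − 28*p*/(1 − *p*) = 4.9 days. With a true mean of 10 days, 6.1% remain ongoing and it is 8.2 days.

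**The case against.** **The scale may be intended.** Clinic visits are not timed to a dose, and a cumulative arm measure is reasonable for repeat dosing. The rating rows already refer to the arm region of all applications. Appendix 6 grades AE severity by the separate definitions in Protocol 8.2.1.3. All of this stands. It defends the measure but not a label that names a different one.

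**Regrading the earlier study is a counterfactual.** Also true. It shows that the two bruising scales cannot be set side by side; it does not measure an error in this trial.

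**A minimum of 26 days is not secure.** Protocol 8.4 leaves follow-up to the investigator's judgment, 8.1 and 8.2.1 end AE collection with the post-study procedures or at early discontinuation, and Table 10 schedules nothing after Visit 10. This stands, so 12 days is the safer floor for completers.

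**Ongoing events are visible in the listings, and the shells may hold a rule.** Fair. That unresolved events drop out is an inference from SAP 6.3, not a stated method.

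**A stronger reading about unscheduled visits.** Because SAP 6.1 keeps unscheduled-visit data out of the summary tables, a reader might infer that the worst grades are hidden. If a subject contacts the site "for worsening or non-resolving reactions, the subject must be seen for an unscheduled visit", and Protocol 6.1.4 requires that the reaction "will be assessed, recorded as an adverse event in the eCRF and followed to resolution". Neither asks for the 0–3 grade. The "Investigator Skin Assessments" row of Table 10 has no unscheduled column, although Protocol 6.2.13 also calls for investigator assessments at each in-clinic visit during treatment. So the documents do not show that such grades exist. The exclusion is a usual, openly stated convention, the data are listed, and the AE still enters the AE tables.

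**Conclusion.** Two minor defects hold.

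1. The investigator grade is a percentage of the outer arm but is labelled as an amount at the application site. For a single dose this follows from the documents alone for any arm of 40 cm² or more. The label is what is wrong; the documents do not show that the whole-arm measure is.
2. The mean time to resolution has no rule for events that Protocol 8.4 expects to end as ongoing. If they drop out, as SAP 6.3 implies, the mean is biased downward. The share unresolved is not given, so the size is unknown. It may be small, since events from earlier doses have months in which to resolve.

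A reader might go further and conclude that skin reactions are under-counted. The documents do not support that. Any grade of 1 or more must be recorded as an AE. Presence and severity are tabulated in the TEAE, maximum-severity and special-interest tables, and the eDiary tables report site-level bruising extent up to 48 hours. No population or AE count is shown to be wrong.

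**What to change.** 1. Use one denominator wording in Appendix 6, Protocol 6.2.13.2 and 6.2.13.3, the endpoint (Protocol 7.1.1, SAP 4.2) and SAP 11.2.2. Label the grades in Table 14.3.2.3 as percent of outer upper arm, with a footnote that they are not comparable with the eDiary bruising categories or the earlier study's bruising scale.
2. Replace or accompany the simple average with the number and percent of eDiary-reported AEs unresolved, plus a Kaplan-Meier summary (median, and percent unresolved at days 7, 14 and 28) that censors ongoing events at last contact. Add it to the table index. It is descriptive, and should note that subjects contribute several events and that durations rest partly on what subjects recall at clinic visits (Appendix 4).
3. Reconcile the follow-up wording in Protocol 3.2.6.1, 6.1.5, 6.1.6, 6.2.13, 8, 8.1, 8.2.1, 8.4 and Appendix 6, which variously ends follow-up at resolution, at stability, with the post-study procedures or at a fixed date. Then state how end and censoring dates are set, including for a stabilized event.
4. Optional: beside the by-visit columns of Table 14.3.2.3, add a worst-grade row that includes graded unscheduled assessments, if such grades were recorded. It rises with the number of assessments, so it should not replace the by-visit columns.

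Cost: wording changes, a few SAP lines and one added table. Items 1 to 3 need no new data collection.
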